8.5 SUBJECT DISPOSITION

Disposition will be summarized by treatment arm for all randomized subjects and will include the number and percentage randomized, the number and percentage who received each dose and the number who completed the trial. The number and percentage of subjects who discontinued will be summarized overall and by reason. The number in each analysis population will also be presented.

8.6 DEMOGRAPHIC AND OTHER BASELINE CHARACTERISTICS

Demographic and baseline data will be summarized with descriptive statistics: mean standard deviation, minimum, median, and maximum values for continuous variables, and percentages for categorical variables, by treatment arm, for the mITT population. Prior and concomitant medications will also be summarized with percentages in this fashion.

8.7 MEDICAL HISTORY

The percentage of subjects with abnormal medical history findings will be summarized by body system, by treatment arm, for the mITT population.

8.8 PRIOR AND CONCOMITANT MEDICATIONS

Prior medications are those that were used before the start of the trial (prior to Day 0). Concomitant medications are those used during the course of the trial (on or after Day 0). Partial start dates of prior and concomitant medications will be assumed to be the earliest possible date consistent with the partial date. Partial stop dates of prior and concomitant medications will be assumed to be the latest possible date consistent with the partial date. Data for all prior and concomitant medications will be summarized with percentages by treatment arm, for the mITT population.

8.9 EFFICACY ANALYSES

The true treatment effect on the primary endpoint is $\delta = p_V - p_P$, where p_V and p_P denote the true population probabilities of the primary endpoint for VGX-3100X and Placebo, respectively. The primary hypothesis of superiority is:

$$H_0$$
: $\delta \leq 0$ vs. H_1 : $\delta > 0$.

A p-value for this hypothesis test and corresponding 95% confidence interval will be computed based on the method of Miettinen and Nurminen [27]. Superiority will be concluded if the one-sided p-value is <0.025 and the corresponding lower bound of the 95% CI exceeds zero.

The secondary efficacy endpoints will be analyzed in the same manner as the primary hypothesis, but without the hypothesis test p-values.

The histopathologic efficacy time frame is defined by those who have undergone a biopsy or surgical excision at any time starting from 14 days prior to the protocol-specified target date of Week 36. It also includes subjects who underwent early intervention prior to this time frame; these subjects are considered as failures for the efficacy endpoints. Table 13 provides details for the definition of the primary endpoint response.

Table 13. Definition of Primary Endpoint Responder and Non-Responder

Responder	Non-Responder
Subject with no histologic evidence of cervical	Subject with histologic evidence of cervical HSIL, AIS, cervical carcinoma at Week 36 evaluation
HSIL ^a at Week 36 evaluation and no evidence of HPV-16 or HPV-18 at Week 36	OR
AND	Subject with evidence of HPV-16 or HPV-18 at Week 36
Subject in which a cervical tissue sample was NOT obtained between collection of tissue to determine entry eligibility up to Week 36 primary endpoint visit	OR
	Subject in which an additional cervical tissue sample was obtained between collection of tissue to determine entry eligibility up to Week 36 primary endpoint visit

^a no evidence of HSIL is defined by histology as negative, squamous atypia, or LSIL

Exploratory analyses will examine the relationship between the primary efficacy endpoint and a) HLA results, b) colposcopy results, c) cytology results, and d) HPV results. As each of these results are categorical, relationships will be examined with contingency tables and logistic regression models which model the primary endpoint versus these results and treatment group as regressor variables.

Other exploratory analyses will examine durability of clearance of HPV-16 and/or HPV-18 infection from cervical tissue at Weeks 62 and 88, and clearance of HPV-16 and/or HPV-18 infection from non-cervical tissue. Descriptive statistics will be utilized; percentages of subjects who cleared will be presented by time point or anatomic location and treatment group.

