8.2 RANDOMIZATION AND BLINDING

Subjects will be randomized (2 VGX-3100X:1 Placebo) in a stratified manner according to a) the degree of CIN observed in the biopsy specimens at screening (CIN2 vs. CIN3), b) BMI category (≤25 vs. >25 kg/m²), and c) age category (<25 years vs. ≥25 years). There will be no pre-determined number of subjects required to be randomized within each stratum. To ensure that milder CIN2 disease is not over-represented in the study, the percentage of subjects enrolled with CIN2 will not exceed 50% of the total enrolled.

The study is double-blinded.

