2 STUDY DESIGN

This Phase 3 study design is based upon the Phase 2b study design and results. HPV-301 is a prospective, randomized, double-blind, placebo controlled study to determine the efficacy, safety, and tolerability of VGX-3100 administered by IM injection followed by EP delivered with CELLECTRA[™] 5PSP in adult women with histologically confirmed cervical HSIL (CIN2, CIN3) associated with HPV-16/18.

A sample of approximately 198 subjects will be randomized to receive either 6 mg (in 1 ml) VGX-3100 or placebo, each IM followed by EP, in a 2:1 ratio. This sample size provides 90% power to declare VGX-3100 superior to placebo, assuming, based upon Phase 2b study results, that the true proportion of subjects whose lesion(s) regress and whose HPV-16/18 clears is 35% and 14% for VGX-3100 and placebo, respectively.

Subjects will be randomized in a stratified manner according to (a) the CIN severity observed in the biopsy specimens at screening (i.e. CIN2 vs. CIN3), (b) BMI category (≤25 vs. >25 kg/m²), and (c) age category (<25 years vs. ≥25 years). To ensure CIN2 disease is not over-represented in the study, the percentage of subjects enrolled with CIN2 will not exceed 50% of the total enrolled.

To be eligible for the study, subjects age 18 years and above must consent to participate and have cervical biopsy/biopsies of the cervical lesion(s) at the time of screening. Slides of the biopsy will be sent to a PAC in a blinded manner to establish the presence of cervical HSIL within screening. In order to be eligible for continued enrollment, the PAC must assign the histologic diagnosis of cervical HSIL. Subjects must also have a cervical specimen test positive for HPV-16/18 by cobas[™] HPV test to be eligible for participation in the study.

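### The primary Miettinen-Nurminen analysis, as last shown, makes no reference to the CIN, BMI and age strata used in randomisation; stratifying it would be a small, free gain in efficiency

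*Protocol*

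**What the plan says.** Protocol Section 8.2, in the last full text shown (taken to be version 2.1, from which the version 3.0 change list starts), reads: "Subjects will be randomized (2 VGX-3100X:1 Placebo) in a stratified manner according to" three two-level factors. These are "the degree of CIN observed in the biopsy specimens at screening (CIN2 vs. CIN3"), BMI split at 25 kg/m², and "age category (<25 years vs. ≥25 years"). That makes 2 × 2 × 2 = 8 strata, with no set number of women in any of them. Section 2 of version 3.0 keeps the scheme: "Subjects will be randomized in a stratified manner according to (a) the CIN severity observed in the biopsy specimens at screening", followed by BMI and age.

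Section 8.9 of the same earlier text defines the effect as δ = p_V − p_P, where the two terms "denote the true population probabilities of the primary endpoint for VGX-3100X and Placebo, respectively". The analysis follows: "A p-value for this hypothesis test and corresponding 95% confidence interval will be computed based on the method of Miettinen and Nurminen". The decision rule is: "Superiority will be concluded if the one-sided p-value is <0.025 and the corresponding lower bound of the 95% CI exceeds zero". Secondary efficacy endpoints are handled in the same way, without p-values. Neither strata nor weights appear.

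The version 3.0 summary of changes lists a move to intention-to-treat with 198 women, missing outcomes counted as failures, and a subgroup analysis by prophylactic-vaccine history. It lists no change to the test or interval. The version 3.0 Section 8.9 is not in the text at hand.

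**The concern.** Stratified randomisation nearly removes chance imbalance between the arms on the stratification factors. An analysis that ignores the strata still carries the between-stratum variation in its standard error. If the factors predict regression and clearance, that standard error is larger than the true sampling variation of the difference. The interval is then wider than it need be, the true one-sided error falls below 2.5%, and some power is forgone.

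There is also a pre-specification point. If Section 8.9 does not say whether the strata enter, with what weights, and what happens in sparse strata, two defensible p-values exist for the same data.

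**Working it through.** **1. Stated power, without strata.** Pooled-variance normal approximation, two-sided 0.05, 2:1 allocation:

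power = Φ{ (δ − 1.96·SE₀) / SE₁ }, with SE₀ = √[p̄(1−p̄)(1/n_V + 1/n_P)] and SE₁ = √[p_V(1−p_V)/n_V + p_P(1−p_P)/n_P].

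- Version 3.0 (Section 2: 198 women, 35% vs 14%): n_V = 132, n_P = 66, p̄ = (2×0.35 + 0.14)/3 = 0.28. SE₀ = 0.0677, SE₁ = 0.0596. Power = Φ{(0.21 − 0.1327)/0.0596} = Φ(1.30) = 90.3%. The exact binomial power of the unstratified Miettinen-Nurminen test is 90.8%.
- Earlier version (Section 8.3: 165 women, 90% evaluable, 40% vs 15%): n_V = 99, n_P = 49.5, p̄ = 0.317. SE₀ = 0.0810, SE₁ = 0.0707. Power = Φ{(0.25 − 0.1587)/0.0707} = Φ(1.29) = 90.2%. The exact power at 99:49 is 90.3%.

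Both stated figures reproduce from the two overall rates alone. The sample size takes no credit for the strata.

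**2. What stratifying would change.** The stratified score statistic is

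z = Σ w_s d_s / √[Σ n_Vs n_Ps p̄_s(1−p̄_s)/(n_s−1)], with w_s = n_Vs n_Ps/n_s.

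Allocation is 2:1 in every stratum, so w_s ≈ (2n_s/3)(n_s/3)/n_s = 2n_s/9. The weights are close to proportional to stratum size, so the weighted difference estimates nearly the same quantity as p_V − p_P. Only the variance changes.

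**3. Simulation.** The documents give no prognostic strength for any factor, so everything here is an assumption: odds ratios as in the table, the same in both arms; 50% CIN2; 50% with BMI above 25; 25% under age 25; permuted blocks of 6; 40,000 trials per scenario. Marginal rates are held at the planned values. Error is evaluated at a common rate of 28% (198 women) or 31.7% (148 evaluable). The row marked * is a separate run of 20,000 trials with 30% under age 25.

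| Odds ratios: CIN, BMI, age | Power, 198 women: unstratified → stratified | Power, 148 evaluable: unstratified → stratified | One-sided error, unstratified (198 / 148) | One-sided error, stratified (198 / 148) |
|---|---|---|---|---|
| 1, 1, 1 | 90.7% → 90.6% | 90.0% → 90.0% | 2.4% / 2.3% | 2.4% / 2.3% |
| 1.5, 1.2, 1.2 | 90.6% → 90.8% | 90.4% → 90.5% | 2.3% / 2.4% | 2.3% / 2.4% |
| 2, 1.5, 1.5 | 90.8% → 91.3% | 90.5% → 91.0% | 2.1% / 2.2% | 2.3% / 2.4% |
| 3, 1.5, 2 * | 91.8% → 92.9% | – | 1.9% / – | 2.3% / – |
| 4, 2, 2 | 91.8% → 93.5% | 91.4% → 93.4% | 1.7% / 1.9% | 2.3% / 2.5% |
| 6, 3, 3 | 92.1% → 95.0% | 91.8% → 95.0% | 1.3% / 1.4% | 2.3% / 2.4% |

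The Monte Carlo standard error of a power near 90% is √(0.9×0.1/40,000) = 0.15 points, so the first two rows show no material difference.

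**4. Sparse strata.** With 66 placebo women in 8 strata the average is 66/8 ≈ 8. If a quarter of women are under 25, each stratum in that age group holds about 198 × 0.5 × 0.5 × 0.25 ≈ 12 women, of whom about 4 are on placebo. Small cells are likely, so a collapsing rule is needed.

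**The case against.** The case on the other side is substantial.

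- **The text never says unstratified.** A reader might infer that the protocol fixes an unstratified test. It does not say so. The named method has a stratified form, and weights and sparse-cell rules are often left to the SAP, which is not shown. Some features favour the unstratified reading: one probability per arm; the same method reused for adverse events (8.11.1) and for the comparison of women with and without excision (8.14); and covariates named in 8.9 only for the exploratory logistic models. These make it likely, not certain.
- **The quoted Section 8.9 is superseded.** Version 3.0 modified Section 8. That the test is unchanged is inferred from a change list that presents itself as covering the significant changes. This limits confidence.
- **A reader might infer that precision already paid for is being discarded.** The documents do not support that. The 90% power counts no gain from strata, and the unstratified test delivers it, with somewhat more in the prognostic scenarios.
- **A reader might infer that the protocol itself declares CIN grade prognostic.** The wording "To ensure that milder CIN2 disease is not over-represented in the study" explains the 50% cap on CIN2, not the stratification. The protocol gives no reason for choosing any of the three factors.
- **Validity is not at stake.** In the simulations the unstratified test errs on the conservative side, so a false claim of superiority is not made more likely.

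All of this stands and sets the level of the point. What remains is that Section 8.9 states a test, an interval and a decision rule without the design strata, when including them costs essentially nothing and may help.

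**Conclusion.** The point holds as a low-severity matter of efficiency and clarity, with medium confidence. Section 8.9 as last shown places the primary p-value and interval on a single overall difference and does not refer to the randomisation strata.

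Read as unstratified, the analysis is valid and adequately powered. Stratifying would gain nothing material if the factors are unrelated to outcome or only weakly related, about 0.5 points of power for moderate effects, and 1 to 3 points for strong to very strong ones. The unstratified one-sided error would be about 2.1% to 2.2% with moderate effects and 1.7% to 1.9% with strong ones, falling to about 1.3% to 1.4% at the extreme of the range tried.

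These sizes rest on assumed odds ratios, stratum shares and block size. The documents do not show that any loss will occur, nor that the planned test is wrong.

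**What to change.** In Section 8.9, and in the SAP to match, state that the primary risk difference, its p-value and its 95% interval use the stratified Miettinen-Nurminen method with Cochran-Mantel-Haenszel weights over the randomisation strata. State that the same applies to the secondary efficacy intervals. Fix before unblinding which strata are merged, and in what order, when a stratum has an empty or very small arm; the documents give no basis for a particular order, so the sponsor should choose and record one. Report the unstratified result as a sensitivity analysis.

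The cost is a sentence or two. No new data are needed, and the sample size can stay as it is because it was computed without credit for strata. If the version 3.0 Section 8.9 or the SAP already specifies this, nothing needs to change beyond checking that the two agree.

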3.4 EXPLORATORY OBJECTIVES AND ASSOCIATED ENDPOINTS

Exploratory Objectives	Associated Endpoints	
Evaluate tissue immune responses to VGX- 3100X in cervical samples	Assessment of markers including but not limited to CD8+ and FoxP3+ infiltrating cells. Additional assessments may include visualization of Granulysin, Perforin, CD137, CD103 and PD-L1 in cervical tissue as sample allows. Markers listed here may change as new relevant information becomes available	
Describe the clearance of HPV-16 and/or HPV-18 infection from anatomic locations outside the cervix	2. Proportion of subjects who have cleared HPV-16 and/or HPV-18 on specimens from outside the cervix (inclusive of oropharynx, vagina and peri-anus) at Week 36 Visit	

Exploratory Objectives	Associated Endpoints		
3. Evaluate effect of HLA type on efficacy	3. HLA (per-locus and per-allele basis) in conjunction with histologic regression of cervical HSIL at Week 36 visit		
4. Describe association of previous colposcopy, cytology and HPV testing results with histologic regression at Week 36	4. Colposcopy, cytology, and HPV test results at Weeks 15 and 28 visits in conjunction with histologic regression of cervical HSIL at Week 36 visit		
5. Describe the durability of virologic clearance of HPV-16 and/or HPV-18 for subjects treated with VGX-3100X compared with those treated with placebo	5. Proportion of subjects with no evidence of HPV-16 and/or HPV-18 by type specific HPV testing at Weeks 62 and 88 visits		
6. Describe the patient-reported outcomes for subjects treated with VGX-3100X	6. The following two questionnaires; Short Form Health Survey, version 2 (SF-36v2 [™]) and EQ-5D-5L [™] will be self-administered prior to first dose (i.e. Day 0), following each dose, and at Weeks 28, 40 and 88 to measure score(s).		

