8 STATISTICAL ANALYSIS PLAN

8.1 GENERAL CONSIDERATIONS

The statistical analysis of the data will be performed by Inovio Pharmaceuticals or its representative.

This is a two-arm, multi-center, placebo-controlled, blinded, and randomized clinical trial in subjects with a histologic diagnosis of cervical HSIL. The study's primary endpoint is binary: regression to CIN1/normal and clearance of HPV-16 and/or HPV-18 infection from cervical tissue based on tissue collected at Week 36. The primary hypothesis is that VGX-3100X will be superior to placebo regarding the proportion who achieve the primary endpoint. Secondary efficacy analyses involve regression to CIN1/normal, clearance of HPV-16 and/or HPV-18 infection from cervical tissue and non-progression of cervical lesions. Other secondary analyses concern safety and humoral and cellular immunological measures. Exploratory analyses concern tissue immunological measures, durability of clearance of HPV-16 and/or HPV-18 infection from cervical tissue, clearance of HPV-16 and/or HPV-18 infection from non-cervical tissue, effect of HLA type on efficacy, association of colposcopy, cytology, and virology and efficacy, and patient-reported outcomes.

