3.4 EXPLORATORY OBJECTIVES AND ASSOCIATED ENDPOINTS

Exp	ploratory Objectives	Ass	ociated Endpoints
1.	Evaluate tissue immune responses to VGX-3100 in cervical samples	1.	Assessment of markers including but not limited to CD8+ and FoxP3+ infiltrating cells. Additional assessments may include visualization of Granulysin, Perforin, CD137, CD103 and PD-L1 in cervical tissue as sample allows. Markers listed here may change as new relevant information becomes available
2.	Evaluate effect of HLA type on efficacy	2.	HLA (per-locus and per-allele basis) in conjunction with histologic regression of cervical HSIL at Week 36 visit
3.	Describe association of microRNA (miRNA) profile, previous colposcopy, cytology and HPV testing results with Week 36 histologic regression	3.	Colposcopy, cytology, and HPV test results (Weeks 8, 15 and 28 visits) and miRNA profile (baseline, Week 8) in conjunction with histologic regression of cervical HSIL at Week 36 visit
4.	Describe the durability of virologic clearance of HPV-16 and/or HPV-18 for subjects treated with VGX-3100 compared with those treated with placebo	4.	Proportion of subjects with no evidence of HPV-16 and/or HPV-18 by type specific HPV testing at Weeks 62 and 88 visits
5.	Describe the patient-reported outcomes for subjects treated with VGX-3100	5.	Patient-reported outcome questionnaires will be self-administered at baseline, Weeks 4, and 12, 8-14 days following each dose, and at Weeks 28, 36, 40 and 88 by subjects enrolled in US, Canada, Mexico, Germany and UK.

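### Section 8.9 (version 2.1) models the composite primary endpoint in the exploratory predictor analyses, although exploratory endpoints 3 and 4 specify histologic regression; for HPV, predictor and outcome then overlap

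*Protocol*

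**What the plan says.** Version 2.1, Section 8.9, defines the exploratory analyses by their outcome: "Exploratory analyses will examine the relationship between the primary efficacy endpoint and a) HLA results, b) colposcopy results, c) cytology results", with HPV results as the fourth item. It plans contingency tables and "logistic regression models which model the primary endpoint versus these results and treatment group as regressor variables".

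The primary endpoint is a composite. Section 8.1: "The study's primary endpoint is binary: regression to CIN1/normal and clearance of HPV-16 and/or HPV-18 infection". Table 13 in Section 8.9 lists, as sufficient for non-response, "Subject with evidence of HPV-16 or HPV-18 at Week 36".

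Section 3.4 of the same version fixes another outcome for these questions. Exploratory endpoint 3 reads "HLA (per-locus and per-allele basis) in conjunction with histologic regression of cervical HSIL at Week 36 visit". Exploratory endpoint 4 covers colposcopy, cytology and "HPV test results at Weeks 15 and 28 visits in conjunction with histologic regression of cervical HSIL at Week 36 visit". Section 2.1 treats the two outcomes as distinct: the composite is primary and histologic regression alone is secondary.

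Version 3.0 renumbers these as exploratory endpoints 2 and 3, adds Week 8 and miRNA, and keeps the outcome: "Colposcopy, cytology, and HPV test results (Weeks 8, 15 and 28 visits) and miRNA profile (baseline, Week 8) in conjunction with histologic regression". Section 8 of version 3.0 is not in the text available.

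**The concern.** The protocol fixes the dependent variable of these models twice and differently. This is not detail left to a later analysis plan: someone following Section 8.9 as written would not produce the analysis that endpoints 3 and 4 describe.

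For HLA, colposcopy and cytology, the fault stops there. For HPV there is a second one. A woman who is HPV-positive at Week 28 and stays positive is a non-responder at Week 36 whatever her histology shows. Part of any link between the earlier HPV result and the composite is therefore persistence of the infection and says nothing about the lesion. Section 2.3 describes the frequent monitoring as an opportunity to explore predictors of efficacy, so an HPV odds ratio from this model is likely to be read as an early marker of lesion regression.

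**Working it through.** **The plan's own figure.** The protocol attaches no number to this analysis. The version 2.1 power statement (165 randomised 2:1, 40% vs 15%, 90% evaluable) reproduces at 0.902 and does not depend on this point.

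**Outcomes side by side (version 2.1).**

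| Predictor | Outcome in Section 3.4 | Outcome in Section 8.9 | Is the predictor's own Week 36 value part of the Section 8.9 outcome? |
|---|---|---|---|
| HLA | histologic regression | composite | no |
| Colposcopy | histologic regression | composite | no |
| Cytology | histologic regression | composite | no |
| HPV (Weeks 15, 28) | histologic regression | composite | yes |

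Section 8.9 gives no visit for the HPV results; Weeks 15 and 28 come from endpoint 4.

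**How the overlap acts.** Let r be the probability of histologic regression and v the probability of being HPV-16/18 negative at Week 36 among regressors, each by earlier HPV status (1 = negative, 0 = positive). The composite rate is r × v, ignoring the interval-tissue rule. The composite risk ratio is (r1/r0) × (v1/v0), so it exceeds the histologic risk ratio whenever v1 > v0. The composite odds ratio is [r1v1/(1 − r1v1)] / [r0v0/(1 − r0v0)].

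**Illustration with r1 = r0 = r, so that the histologic odds ratio is 1.** The protocol gives no persistence rates, so every v is an assumption. Set A takes r = 0.50. Set B chooses r so that r × (Phase 2b Week 36 clearance) equals the design rate. Clearance comes from Table 8: VGX-3100 (19 + 36)/(46 + 57) = 55/103 = 0.534; placebo (6 + 5)/(21 + 17) = 11/38 = 0.289. Then r = 0.40/0.534 = 0.749 and r = 0.15/0.289 = 0.518.

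| Set | r | v1 / v0 | Composite rates | Composite OR |
|---|---|---|---|---|
| A | 0.50 | 0.90 / 0.25 | 45.0% vs 12.5% | 5.7 |
| A | 0.50 | 0.95 / 0.15 | 47.5% vs 7.5% | 11.2 |
| A | 0.50 | 0.95 / 0.10 | 47.5% vs 5.0% | 17.2 |
| B, VGX | 0.749 | 0.9 / 0.3 | 67.4% vs 22.5% | 7.1 |
| B, VGX | 0.749 | 0.8 / 0.4 | 59.9% vs 30.0% | 3.5 |
| B, VGX | 0.749 | 0.7 / 0.5 | 52.4% vs 37.5% | 1.8 |
| B, placebo | 0.518 | 0.9 / 0.3 | 46.6% vs 15.5% | 4.8 |
| B, placebo | 0.518 | 0.8 / 0.4 | 41.5% vs 20.7% | 2.7 |
| B, placebo | 0.518 | 0.7 / 0.5 | 36.3% vs 25.9% | 1.6 |

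Worked line: (0.475/0.525)/(0.075/0.925) = 11.2. The range is about 1.6 to 17.

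**Is a histologic odds ratio of 1 realistic?** Phase 2b, VGX-3100 arm:
- Week 36 clearance: 55/103 = 0.534 (Table 8).
- Regression: about 53/107 = 0.495. This is regressors with Week 62 HPV data (Section 2.4) over the Week 62 HPV total of 56 + 51 in Table 8, so denominators are mixed and the figure is approximate.
- Independence would give a composite of 0.534 × 0.495 = 0.264, about 26%. Section 2.1 reports 39.5%.
- The 2 × 2 shares these margins imply are: both 0.395; regression only 0.100; clearance only 0.139; neither 0.366. Odds ratio = (0.395 × 0.366)/(0.100 × 0.139), about 10.

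That association is cross-sectional at Week 36 and does not come from Week 15 or 28, but it makes a true value of 1 unlikely. Set B shows the same strain: independence needs 75% regression in the active arm to reach 40%. Once the histologic association differs from 1, the excess on the odds-ratio scale also depends on the regression rates and cannot be read from the table.

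**The case against.** The best defence is that the composite is this trial's definition of efficacy. The HLA objective asks about an effect on efficacy, Section 8.1 describes the association of colposcopy, cytology and virology with efficacy, and Section 2.3 speaks of predictors of efficacy. On that reading Section 8.9 agrees with Section 8.1. This stands in part: the conflict is with the endpoint column of Section 3.4, and with objective 4, which names histologic regression outright. It is not with every stated objective.

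Secondly, version 3.0 supersedes version 2.1, and its summary of changes says Section 8 was modified. The changes it lists there (missing data as failure, a subgroup by prophylactic vaccine history) do not touch this analysis, but the list is limited to significant changes. Whether the current Section 8.9 has the fault cannot be settled from the text available.

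Thirdly, predicting the trial's own responder status from interim HPV results is a legitimate question. That also stands, provided the outcome is labelled.

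A reader might go further and infer that the HPV finding would be a pure artefact, with an odds ratio near 11 where nothing exists. The documents do not support this. The figure rests on assumed persistence and on a true odds ratio of 1, which the Phase 2b results make implausible; Section 2.4 itself links clearance with colposcopic signs of regression. Nor are all the predictors circular: HLA, colposcopy and cytology are not components of the composite. And no miRNA model appears in the Section 8.9 that can be read.

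**Conclusion.** The point holds for version 2.1 as a contradiction between Sections 8.9 and 3.4. All four predictor analyses use an outcome other than the one their endpoints specify. Only for HPV does this also distort the association, because Week 36 HPV-16/18 negativity sits inside the outcome. As a risk ratio the inflation follows whenever earlier clearance tends to persist among regressors. As an odds ratio, with no histologic association, it ranges from about 1.6 to 17 under the assumed persistence values. The sounder reading is that the composite would overstate a probably real association and leave its histologic part unidentifiable.

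The consequence is minor. The analyses are exploratory, and the primary test, the one-sided 0.025 level and the sample size are untouched.

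**What to change.** In Section 8.9, name histologic regression at Week 36 (no HSIL as defined in footnote a of Table 13) as the dependent variable of the exploratory contingency tables and logistic models. Keep the existing rule that early intervention counts as failure, and carry over the visits from the exploratory endpoint. If the composite is wanted, show it as a labelled additional analysis, with a note that for HPV the predictor and the outcome overlap.

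Check Section 8.9 of version 3.0 for the same mismatch, including any miRNA model, since its exploratory endpoints still specify histologic regression.

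The cost is one phrase in Section 8.9 and the matching line in the analysis plan. No new data are needed: Week 36 histology is already collected and read by the Pathology Adjudication Committee.
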